- Acute or chronic signs of ischemia
- Left Bundle Branch Block
- Prior myocardial infarction

Open-Label Extension

Inclusion Criteria:

1. Subject must be able to comprehend and willing to sign the OLE Informed Consent/Accent Form (ICF).
2. Subject must continue to meet the entry criteria from the double-blind period. The SALT score and duration of disease are based on the double-blind period baseline visit.
3. Subject has not experienced any clinically significant AEs, SAEs or tolerability issues that met study discontinuation criteria in the double-blind period.
4. Subject is capable of regrowing scalp hair in the opinion of the investigator.
5. WOCBP must have a negative UPT at entry into OLE.

Duration of Treatment

Double-blind Period

The duration of the screening period could be up to 30 days. Once randomized, the maximum duration of study treatment is from Baseline (Visit 2) to the Post-treatment follow-up visit at Week 28 (Visit 11) is anticipated to be a maximum of 200 days (197 days + 3-day window).

Open-Label Extension

The maximum duration of the of study treatment in the OLE is 176 days (169 days + 7-day window). The maximum duration of the study participation from entry into the OLE to completion of the post-treatment follow up visit is 204 days.

Endpoints

Primary Efficacy:

- Percent change from baseline in the Severity of Alopecia Tool (SALT) score at Week 24 (Visit 10), also described as mean percent regrowth

Secondary Efficacy:

- Percent change from baseline in the Alopecia Density and Extent Score (ALODEX) score at Week 24 (Visit 10), also described as mean percent regrowth
- Mean change from baseline in SALT score at Week 24 (Visit 10)
- Mean change from baseline in ALODEX score at Week 24 (Visit 10)
- Proportion of subjects in each treatment arm achieving $\geq 50\%$ hair regrowth compared with baseline using a separate model for SALT and for ALODEX scores
- Change from baseline in the Alopecia Scalp Appearance Assessment (AAA) for Patchy AA (Patient-reported outcome [PRO]) at Week 24 (Visit 10)
- Change from baseline in the Alopecia Scalp Appearance Assessment (AAA) for Patchy AA (Clinician-reported outcome [ClinRO]) at Week 24 (Visit 10)
- Change from baseline in the Physicians Global Impression of Severity (PhGIS) of Patchy AA at Week 24 (Visit 10)
- Change from baseline in the Subject Global Impression of Severity (SGIS) of Patchy AA at Week 24 (Visit 10)

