5.9. Subject Withdrawal Criteria

Subjects will be informed that they are free to withdraw from the study at any time and for any reason. The investigator may remove a subject from the study if, in the investigator's opinion, it is not in the best interest of the subject to continue the study. Examples of other reasons subjects may be discontinued from the study are: a change in compliance with an inclusion or exclusion criterion, occurrence of AEs, occurrence of pregnancy, use of a prohibited therapy or subject is unwilling or refuses to continue with the protocol defined study visits and/or subject withdraws consent/ assent (Refer to Section 9.2.4 for study medication discontinuation or termination criteria).

In case of premature discontinuation from double-blind study participation, all efforts will be made to perform all Visit 10 (Week 24) assessments. For premature discontinuations occurring in the OLE, all efforts will be made to perform all OLE Visit 6 assessments. The date the subject is withdrawn from the study and the reason for discontinuation must be recorded in the subject's electronic case report forms (eCRFs). All withdrawn subjects with ongoing AEs will be followed until the event has resolved or stabilized, until the subject is referred to the care of a local health care professional, or until a determination of a cause unrelated to the study medication or study procedures is made.

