8.3. Assessment of Subject Satisfaction and Patchy AA Impact

8.3.1. Subject Global Impression of Treatment Satisfaction

The investigator or study staff will instruct the subject to answer this questionnaire in relation to their satisfaction with the outcome of the study medication response. Subjects will assess their satisfaction with the outcome of the study treatment in all treated patchy areas on a 7-point satisfaction scale from extremely satisfied to extremely dissatisfied at Week 12 (Visit 7) Week 24 (Visit 10), and if continuing in the open label extension, OLE Visit 5.

(APPENDIX 8).

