**3.3.7. Presentations by Study Visit**

Results from efficacy assessments and safety will be summarized by study visit and treatment group. For the DB period, all assessments will be assigned to an analysis visit window using the study day ranges described in Table 1. All study days up to and including Day 1 (DB) are considered the baseline eligible analysis visit window. The last non-missing assessment in the baseline analysis visit window will be used for the baseline summary presentations. If assessments are collected multiple times within a given analysis visit window, the result closest to the target study day, regardless of whether scheduled or unscheduled, will be used for summary presentations. If two measurements have the same distance to the target study day, the first assessment will be used in the summary presentations. All assessments will be presented in the listings.

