**Table 1: Visit Windows**

Nominal Visit	Target Study Day	Analysis Visit	Study Day Range
Screening	-30 to -1	Baseline	<=1
Day 1	1		
Week 1	8	Week 1	[2 – 11]
Week 2	15	Week 2	[12 – 22]
Week 4	29	Week 4	[23 – 42]
Week 8	57	Week 8	[43 – 70]
Week 12	85	Week 12	[71 – 98]
Week 16	113	Week 16	[99 – 126]
Week 20	141	Week 20	[127 – 154]
Week 24	169	Week 24	[155 to 182]

For the OLE, the analyses will be based on the nominal study visit as reported on the CRF.

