#### **5.2.9. Open-Label Extension**

For the open label extension period, efficacy will be evaluated based on the SALT, ALODEX, Scalp-ClinRO, Scalp-PRO, and SGITS. Descriptive summary statistics will be reported for the following:

- SALT score and change from baseline
- ALODEX Score and change from baseline
- Number (%) of subjects for each category of the Scalp-ClinRO (target patch and entire scalp)
- Number (%) of subjects for each category of the Scalp-PRO (target patch and entire scalp)
- Number (%) of subjects for each category of SGITS.

Summaries will include changes from baseline (study day 1) and changes from the end of the DB study (Visit 10). All by visit summaries will utilize the normal study visit based on CRF collection.

The efficacy summaries will be presented for the following subject groups based on the DB treatment assignments and the duration since end of DB period:

- Subjects who were randomized to Vehicle in the double-blind portion of the study
- Subjects who were randomized to ATI-50002 12% in the double-blind portion of the study who also entered the OLE less than 7 days from the end of their DB treatment period
- Subjects who were randomized to ATI-50002 12% in the double-blind portion of the study who also entered the OLE more than 7 days, but less than 60 days from the end of their DB treatment period
- Subjects who were randomized to ATI-50002 12% in the double-blind portion of the study who also entered the OLE at least 60 days from the end of their DB treatment period
- Subjects who were randomized to ATI-50002 46% in the double-blind portion of the study who also entered the OLE less than 7 days from the end of their DB treatment period

- Subjects who were randomized to ATI-50002 46% in the double-blind portion of the study who also entered the OLE more than 7 days, but less than 60 days from the end of their DB treatment period
- Subjects who were randomized to ATI-50002 46% in the double-blind portion of the study who also entered the OLE at least 60 days from the end of their DB treatment period.

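### Early leavers from the OLE get the post-treatment visit's assessments and the OLE is tabulated by nominal visit, so exit data can enter the Week 28 off-drug row; those leaving before OLE Visit 5 give no OLE satisfaction rating

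*Protocol*

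**What the plan says.** - **Exit visit.** Protocol Section 5.9 handles the two periods differently. Double-blind: "In case of premature discontinuation from double-blind study participation, all efforts will be made to perform all Visit 10 (Week 24) assessments". Visit 10 is the last visit on treatment. OLE: "For premature discontinuations occurring in the OLE, all efforts will be made to perform all OLE Visit 6 assessments".
- **What OLE Visit 6 is.** Both schedules of assessments put OLE Visit 5 at Week 24, Day 169, as the last treatment visit. OLE Visit 6 stands under the post-treatment heading at Week 28, Day 197. The Protocol synopsis agrees: "The maximum duration of the study participation from entry into the OLE to completion of the post-treatment follow up visit is 204 days", which is 197 plus the 7-day window.
- **Visit assignment.** SAP Section 3.3.7, double-blind: "For the DB period, all assessments will be assigned to an analysis visit window using the study day ranges described in Table 1". For the extension, the line under Table 1 reads: "For the OLE, the analyses will be based on the nominal study visit as reported on the CRF". SAP Section 5.2.9 repeats the rule: "All by visit summaries will utilize the normal study visit based on CRF collection", where the word normal appears to stand for nominal.
- **Satisfaction rating.** Protocol Section 8.3.1 schedules SGITS at Weeks 12 and 24 of the double-blind period and, "if continuing in the open label extension, OLE Visit 5". The SAP schedule agrees. The Protocol's OLE schedule is hard to read by column in the extracted text, but nothing places SGITS at OLE Visit 6. SAP Section 5.2.9 lists SGITS among the OLE efficacy summaries.
- **Related rules.** SAP Section 3.3.4 applies LOCF to missing assessments, including those after early termination, without saying whether this reaches the OLE. SAP Section 3.3.6 sets Day 1 (OLE) at the Visit 10 date for everyone entering the OLE. Protocol Section 5.5 instead dates the start of OLE treatment from OLE Visit 1.

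**The concern.** The two exit rules in Section 5.9 look parallel but are not. A double-blind leaver has the end-of-treatment assessments, and the SAP files them in the week they were done. An OLE leaver has the assessments of a visit meant to show what happens off drug, and the SAP files them by visit label. Unless the CRF separates exits, the Week 28 row would combine subjects who finished treatment about four weeks before with subjects measured at or near their last dose, in any week of the OLE. This affects the summaries of SALT, ALODEX, Scalp-ClinRO, Scalp-PRO, laboratory values and vital signs.

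The satisfaction rating has a separate gap. It is not part of OLE Visit 6, so a subject who leaves before OLE Visit 5 has the exit visit but is not asked the question. The OLE satisfaction table then describes only those who stayed to Week 24.

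At stake is how the long-term efficacy and safety tables are read. No hypothesis test is involved.

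**Working it through.** The plan gives no figure for this point, so the check compares the rules and then sizes the effect under stated assumptions.

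**1. Is OLE Visit 6 an off-drug visit?** Scheduled gap from OLE Visit 5: 197 - 169 = 28 days. With the ±7-day windows, the shortest gap is (197 - 7) - (169 + 7) = 14 days and the longest is (197 + 7) - (169 - 7) = 42 days. A completer's Visit 6 is therefore planned for 14 to 42 days after the last treatment visit. An early leaver's exit visit has no such gap built in.

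**2. Same event, two periods.**

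| | Double-blind leaver, Day 43 | OLE leaver, OLE Day 43 |
|---|---|---|
| Assessments done | Visit 10 (end of treatment) | OLE Visit 6 (post-treatment) |
| Placed by | study day, Table 1 | nominal CRF visit |
| Row entered | Week 8, range 43-70 | Week 28, if labelled OLE Visit 6 |

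**3. What windows in the style of Table 1 would do.** Midpoints of the OLE target days: (15 + 29)/2 = 22; (29 + 85)/2 = 57; (85 + 169)/2 = 127; (169 + 197)/2 = 183. Treating boundary days as Table 1 does gives Week 2 = 2-22, Week 4 = 23-56, Week 12 = 57-126, Week 24 = 127-182, and Week 28 from 183. The Day 43 exit then falls in the Week 4 row.

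**4. Why the anchor matters.** With Day 1 (OLE) at Visit 10, a subject whose first open-label application is 60 days later starts on period day 61. OLE Visit 3 (treatment day 29) then falls on period day 61 + 28 = 89, inside the Week 12 window. SAP Section 5.2.9 itself has groups entering at least 60 days after double-blind treatment, so windows on the present Day 1 (OLE) would misplace their data.

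**5. Size of the shift in the Week 28 mean.** Shift = (share of OLE Visit 6 records from early leavers) × (mean difference between leavers' exit values and true Week 28 values). Neither input is in the documents. Assumed ranges are 10-40% and 5-20 SALT points.

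| Share | 5 points | 10 points | 20 points |
|---|---|---|---|
| 10% | 0.5 | 1.0 | 2.0 |
| 20% | 1.0 | 2.0 | 4.0 |
| 30% | 1.5 | 3.0 | 6.0 |
| 40% | 2.0 | 4.0 | 8.0 |

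The OLE tables are split into seven groups, six of them from the active arms. If all 80 active-arm subjects entered and divided evenly (an assumption), each group would hold about 80/6 ≈ 13. Two leavers at 0 among 13, with the other 11 at -20, give 11 × (-20)/13 = -16.9, a shift of 3.1 points.

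**6. SGITS.** The only OLE rating is at Visit 5, so a leaver before Visit 5 contributes none. If LOCF were applied, the value carried forward would be the double-blind Visit 10 rating. For a vehicle subject, that is a rating of vehicle shown under open-label active drug.

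**The case against.** The strongest reply is that Section 5.9 names a set of procedures, not a CRF label. The SAP follows the visit as reported on the CRF, and exits may carry an early-termination or unscheduled label. This stands as a limit on certainty: the mislabelling is inferred. However, neither document defines such a label for OLE assessments. The early-termination entry in the SAP's list of listings concerns disposition.

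Choosing OLE Visit 6 for exits is also defensible. It carries the end-of-OLE physical examination, the only scheduled OLE ECG, laboratory tests, SALT, ALODEX and both scalp ratings. Of the outcome assessments planned for the OLE, only SGITS is lost. That is a reason to keep the visit content and change the filing.

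Third, day windows alone do not cure the satisfaction gap. A rating taken at a Week 6 exit would fall in the Week 4 row, and the Week 24 row would still hold only those who stayed. This is correct and shapes the fix.

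Three stronger readings are tempting but unsupported:

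- **A false post-treatment relapse of 4 to 8 points.** This follows if 20-40% leave, leavers sit at 0, completers hold -20 at both visits, every leaver attends an exit visit labelled OLE Visit 6, and LOCF is not used. Visit 5 then reads -20 and Visit 6 reads -16 to -12. If the general LOCF rule reaches the OLE, the same leavers enter the Visit 5 row at 0, both rows read -16 to -12, and the relapse is zero. The mixing within the Week 28 row remains.
- **Early leavers never have drug collected or compliance checked.** Collection and the check are scheduled at OLE Visits 2 to 5. Protocol Section 7.3 has subjects bring bottles to every visit, and Section 7.7 requires return of all bottles. Only a scheduled check at OLE Visit 6 is absent.
- **The satisfaction table is biased in the drug's favour.** It is plausible that leavers are less satisfied, but the documents do not say so.

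**Conclusion.** The point holds as an inconsistency between the OLE exit rule and the OLE visit-assignment rule, and as a gap in collecting SGITS. The first part is conditional on exits being entered as OLE Visit 6, which is the natural reading but cannot be confirmed without the CRF. The phrase on drug should be read as at or near the last dose, since some leavers may have stopped before the exit visit.

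The size is not determined by the documents. Under the assumed ranges, the Week 28 SALT mean shifts by about 0.5 to 8 points, in a direction that depends on how leavers differ from completers. How it shows across rows depends on whether LOCF applies in the OLE. The SGITS gap needs no such assumption: before OLE Visit 5, no OLE rating is scheduled.

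The consequence is bounded. OLE efficacy is uncontrolled and descriptive, and the Week 24 primary analysis and other double-blind analyses are untouched. The change is worth making because it is cheap and these tables are the planned answer to the long-term objective.

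**What to change.** 1. **SAP Sections 3.3.7 and 5.2.9.** Assign OLE assessments by days since the first open-label application, with windows built as in Table 1. Keep only true post-treatment visits in the Week 28 row, checked against the date of last dose. Amend Day 1 (OLE) in Section 3.3.6, now the Visit 10 date, to match this anchor. State whether LOCF applies in the OLE; if it does, it should not refill the Week 28 row with leavers' values. That row will then describe only those who reached the post-treatment visit, and its number of subjects should be read with it.
2. **Protocol Section 5.9.** Keep the OLE Visit 6 assessments at early exit and add SGITS. Report it in a separate last-on-OLE summary (OLE Visit 5 or early exit), so that leavers are counted.

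The cost is a little more programming and a one-item questionnaire at a visit already held. The reassignment in item 1 relies on assessment and dosing dates, so it can go ahead even if the protocol sentence can no longer be changed.

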5.10. Study Termination

This study may be terminated prematurely in whole or in part due to a change in the benefit/risk profile for ATI-50002 Topical Solution such that continuation of the study would not be justified on medical or ethical grounds. This determination may be made by the Study Investigators in conjunction with the Sponsor, or by IRB or the U.S. Food and Drug Administration (FDA). The Sponsor may also elect to terminate the study if enrollment is sufficiently slow to prevent the completion of the study in an acceptable timeframe, or if ATI-50002 development is discontinued.

If the study is terminated prematurely, the Sponsor will notify the Study Investigators and the FDA. The Investigator must promptly notify all enrolled subjects and the IRB of study termination.

6. INVESTIGATIONAL PLAN

6.1. Overall Study Design

This Phase 2, multicenter, randomized study is designed to evaluate the safety, tolerability and efficacy of ATI-50002 Topical Solution in subjects with stable patchy alopecia areata (AA). Subjects will be required to have a clinical diagnosis of alopecia areata (AA) with at least 15% up to 95% total scalp hair loss for a duration of the current episode of scalp hair loss of a minimum of 6 months and a maximum of 12 years.

During the screening period, subjects will be assessed for eligibility into the study. Subjects will apply up to a maximum of 4 mLs of study medication to the entire scalp twice a day for up to 24 weeks in the double-blind period. Subjects who continue onto the OLE will apply ATI-50002-Topical Solution, 0.46% twice-daily for 24 weeks to the scalp and if applicable to eyebrow(s). Assessment of response to treatment will be performed at Week 4 (Visit 5), Week 8 (Visit 6), Week 12 (Visit 7), Week 16 (Visit 8), Week 20 (Visit 9), Week 24 (Visit 10), post-treatment Week 28 (Visit 11, if applicable), and OLE Visits 3-6. Safety and tolerability will be evaluated at each study visit by assessment of adverse events and vital signs, and at select visits, ECGs and clinical laboratory tests.

6.2. STUDY PROCEDURES

The investigator, a designated and appropriately trained staff member, or the subject will perform the study assessments according to the schedule of assessments (Section 6.3). The same staff member should perform the assessments for a given subject throughout the study. If this becomes impossible, an appropriate designee with overlapping experience with the subject and study should perform the assessments. The same lighting conditions and subject positioning should be used for all evaluations for a given subject.

6.3. Schedule of Assessments

Double-Blind Period	Screening	Baseline	Treatment									Post-Treatment
	Visit 1	Visit 2	Visit 3	Visit 4	Visit 5	Visit 6	Visit 7	Visit 8	Visit 9	Visit 10 ¹⁴	Visit 11 ¹⁴	
Week	0	1	2	4	8	12	16	20	24	28		
Treatment Day	-30 to 0	1	8	15	29	57	85	113	141	169	197	
Treatment Window(days)	N/A	N/A	± 3	± 3	± 3	± 3	± 3	± 3	± 3	± 3	± 3	
Informed consent/ assent ¹	X									X ¹⁴	X ¹⁴	
Inclusion/exclusion criteria	X	X										
Physical exam ²	X									X		
Demographics & medical history	X											
Alopecia Areata History	X											
Vital signs ³	X	X	X	X	X	X	X	X	X	X	X	
Clinical CBC, Chemistry, Virology, Serum Pregnancy, Urinalysis ⁴	X ⁴	X		X	X	X	X	X	X	X	X	
Urine pregnancy test ⁵		X			X	X	X	X	X	X	X	
ECG	X	X		X	X	X	X	X	X	X	X	
SALT Score (prior to ALODEX) ⁶	X			X	X	X	X	X	X	X	X	
ALODEX Score (after SALT) ⁷	X			X	X	X	X	X	X	X	X	
Target Scalp Patch Identification ⁸	X											
Assessment of hair quality ⁹	X			X	X	X	X	X	X	X	X	
Alopecia Appearance Assessment (AAA): Clinician Rating (CR)		X		X		X				X		
All Patches, Target Patch¹⁰												
Alopecia Appearance Assessment (AAA): Subject Rating (SR)		X			X		X			X		
All Patches, Target Patch¹⁰												
Physician Global Impression of Severity (PhGIS) ¹⁰	X			X		X				X		
Physician Global Impression of Change (PhGIC)										X		
Subject Global Impression of Severity (SGIS) ¹⁰	X			X		X				X		
Subject Global Impression of Change (SGIC)										X		
Subject Global Impression Treatment Satisfaction (SGITS)						X				X		
DLQI ¹⁰	X			X		X				X		
Alopecia Impact Assessment (AIA): Subject Rating ¹⁰	X			X		X				X		
Photography (complete scalp and target patch) ¹⁰	X			X	X	X	X	X	X	X	X	
Subject randomization	X											
Subject instructions ¹¹	X	X	X	X	X	X	X	X	X	X		
Dispense, collect, weigh study medication, assess compliance ¹²	X	X	X	X	X	X	X	X	X	X		
In office study medication application ¹³	X											
Concomitant therapies	X	X	X	X	X	X	X	X	X	X	X	
Adverse events	X	X	X	X	X	X	X	X	X	X	X	

Double-Blind Period	Screening	Baseline	Treatment								Post-Treatment
	Visit 1	Visit 2	Visit 3	Visit 4	Visit 5	Visit 6	Visit 7	Visit 8	Visit 9	Visit 10 ¹⁴	Visit 11 ¹⁴
Week	0	1	2	4	8	12	16	20	24	28	
Treatment Day	-30 to 0	1	8	15	29	57	85	113	141	169	197
Treatment Window(days)	N/A	N/A	± 3	± 3	± 3	± 3	± 3	± 3	± 3	± 3	± 3
Select Sites Only¹⁶											
4 mm Punch biopsy ¹⁷		X			X					X	
Suture removal, if applicable ¹⁸ (Approximately 2-weeks after punch biopsy)				X	X ¹⁶					X ¹⁶	
Blood for immunologic studies ¹⁹		X			X					X	
Schedule Telephone Call to occur the Day Prior to Visit 5, and Visit 10 ²⁰				X					X		

Open-Label Extension	Open-Label Treatment						Post-Treatment	
	OLE Visit 1		OLE Visit 2	OLE Visit 3	OLE Visit 4	OLE Visit 5		
Week	OLE Visit 1 occurs at Visit 10 or 11	Visit 11 (Week28) was:		2	4	12	24	28
Treatment Day		≤ 30 Days	> 30 Days	15	29	85	169	197
Treatment Window(days)	NA	NA	NA	± 3	± 3	± 7	± 7	± 7
Informed Consent/ Assent	X	X	X					
Inclusion/exclusion criteria	X	X	X					
Physical exam ²			X					X
Medical History Update			X					
Vital signs ³		X	X	X	X	X	X	X
Clinical CBC, Chemistry, Virology, Serum Pregnancy, Urinalysis ⁴			X	X	X	X	X	X
Urine pregnancy test ⁵		X	X	X	X	X	X	X
ECG								X
SALT Score (prior to ALODEX) ⁶		X ¹⁵	X		X	X	X	X
ALODEX Score (after SALT) ⁷		X ¹⁵	X		X	X	X	X
Alopecia Appearance Assessment (AAA): Clinician Rating (CR)						X	X	X
All Patches, Target Patch								
Alopecia Appearance Assessment (AAA): Subject Rating (SR)						X	X	X
All Patches, Target Patch								
Subject Global Impression Treatment Satisfaction (SGITS)						X		
Photography (complete scalp and target patch)			X ¹⁵		X	X	X	X
Subject instructions ¹¹	X	X	X	X	X	X		
Dispense and weigh study medication ¹²	X	X	X	X	X	X (Weigh only)		
Collect study medication, assess compliance			X	X	X	X		
Concomitant therapies			X	X	X	X	X	X
Adverse events			X	X	X	X	X	X

¹A written, signed ICF/ assent must be obtained from each subject prior to performing any study related procedure (i.e., prior to performing vital signs, standardized photography, biopsies, clinical laboratory sampling or urine pregnancy tests.) An OLE ICF must be obtained prior to performing any OLE assessments.

² A physical exam includes: general appearance, extremities, examination of head, eyes, ears, nose and throat, respiratory, cardiovascular, abdominal, neurological, musculoskeletal, lymphatic and skin assessment.

³Vitals signs include: oral or ear temperature, blood pressure, heart rate, respiration rate (height and weight at baseline only).

⁴ Clinical laboratory sampling include: CBC, Chemistry with lipids, Urinalysis. Quantiferon Gold, HIV, Hepatitis B and C, and Serum Pregnancy should be done at screening visit only.


⁵ UPT must be performed in WOCBP prior to randomization at Baseline (Visit 2) and must be negative for the subject to continue in the study. UPTs in WOCBP must also be obtained at Visits 5, 6, 7, 8, 9, 10, 11 and if applicable, OLE Visit 1, and OLE Visit 2-6. WOCBP must have a negative serum pregnancy test at Screening (Visit 1) and a negative UPT at baseline (Visit 2) prior to randomization. WOCBP must have a negative UPT prior to continuation into the OLE.

⁶ SALT score must be determined prior to ALODEX using device provided. At Baseline (Visit 2), SALT score should be determined prior to application of study medication.

⁷ ALODEX score determined after SALT score using device provided. At Baseline (Visit 2), ALODEX score should be determined prior to application of study medication.

⁸ The subject will be instructed to identify the most bothersome patchy area- this will be the Target Patch. At Baseline (Visit 2), the Target Patch should be identified prior to application of study medication.

⁹ The investigator will assess active hair loss through the hair pull test and the presence of exclamation point hairs. At Baseline (Visit 2), the assessment should be determined prior to application of study medication.

¹⁰ At Baseline (Visit 2), study assessments must be performed prior to application of study medication.

¹¹ The study staff must instruct the subject to apply study medication according to the instructions in APPENDIX 1, 2 and 3.

¹² The study staff must weigh the study medication bottle(s) with cap prior to dispensing to the subject and after the study medication bottles are returned to the investigational site. Staff should review the usage based on the weight of the bottle and counsel the subject as necessary.

¹³ At Baseline (Visit 2), the first application of study medication should be performed by the subject under the supervision of the study staff and the subject should be observed for 20 minutes after the initial application.


¹⁴ At Week 24 (Visit 10) or Week 28 (Visit 11), the subject may be given the option to move into the OLE treatment.
 
• If the subject declines the OLE, Visit 11 (Post-treatment) will be the last double-blind study visit.• If the subject chooses to continue into the OLE, she/he must sign an OLE ICF, complete Visit 10 or Visit 11 as appropriate and OLE Visit 1, prior to being dispensed open-label drug and receiving study medication application instructions. The subject will be scheduled for OLE Visit 2.• If the subject enrolls in open-label treatment within 30 days of completion of Week 24 (Visit 10) or Week 28 (Visit 11), OLE Visit 1 will be conducted to obtain consent/assent and perform the procedures in the Schedule of Assessments. This will be considered the official date that the subject initiated OLE treatment.• If the subject enrolls in open-label treatment > 30 days after completion of Week 28, OLE Visit 1 will be conducted to obtain consent/ assent, and complete the procedures detailed in the Scheduled of Events. This will be considered the official date that the subject initiated OLE treatment and the scheduling of subsequent visits will be based on this date.

¹⁵ SALT, ALODEX and Photography is performed at OLE Visit 1 (if Week 28 is < 30 days) only if there is a significant change from the last double-blind study visit.

Select Sites Only¹⁶

¹⁶ At Baseline (Visit 2) the scalp biopsy and blood samples for immunologic evaluations must be performed prior to study medication application. At Week 4 (Visit 5), and Week 24 (Visit 10), the scalp biopsy and blood samples for immunologic evaluations must be performed prior to study medication application. The evening prior to the Week 4 (Visit 5), and Week 24 (Visit 10) visits, the subject should be instructed to apply study medication approximately 12 hours prior to Week 4 (Visit 5), and Week 24 (Visit 10) visit time and to note the time of application. Subjects should be instructed not to apply study medication before the Week 4 (Visit 5), and Week 24 (Visit 10) visits.


¹⁷ The biopsy will be performed by the investigator or designee using a 4mm punch biopsy per instructions in APPENDIX 11. The Baseline/Day 1 (Visit 2) biopsy must be obtained prior to the first application of study medication. Subjects must be instructed not to apply study medication to the biopsy site until instructed to by the investigator or designee. Study assessments including photography should be completed prior to the biopsy. (Select sites only)

¹⁸ Sutures will be removed approximately 2 weeks following biopsy unless absorbable sutures are used precluding the need for suture removal. (Select sites only)

¹⁹ Blood samples for immunologic studies will be obtained prior to study medication application on Baseline (Day 1/ Visit 2), Week 4 (Visit 5), and Week 24 (Visit 10). (Select sites only)

²⁰ A member of the study staff should schedule a reminder call with the subject to occur on the day before Week 4 (Visit 5), Week 8 (Visit 7), and Week 24 (Visit 10) to remind the subject to apply the study medication approximately 12 hours prior to the visit and to hold the morning dose of study medication. The subject should be instructed to document the time of application and quantity of the dose applied.

